## Study Protocol and Statistical Analysis Plan

### Summary

The purpose of this pilot study is to assess obese clients for two phenotypes, those testing positive and those testing negative for Food Addiction (FA) (Yale Food Addiction Scale, YFAS) and determining the efficacy of four treatments: usual care (IC, dietary and physical activity instruction), individual motivational interviewing alone (MI), individual MI with pharmacotherapy (MI+P) for improving outcome measures within each phenotype, and pharmacological therapy (P).

### Background/significance

The ongoing epidemic of obesity is of great concern, especially among rural Americans, where the rate of obesity is greater than that of Americans living in urban areas. The costs related to obesity and its comorbidities continues to rise and includes the psychological implications of obesity. Scotts Bluff has an overweight/obesity rate of 71% according to the 2014 Scotts Bluff County Health Dept Community Health Assessment. Recently it has been suggested that addiction-like tendencies toward foods, (especially highly processed foods that are high in fat and sugars) (HPFS) is contributing to the epidemic (Schulte 2015, Flint 2014, Iozzo, 2012; Pursey, 2014). In order to assess addictive-like eating behavior, the Yale Food Addiction Scale (YFAS) has been developed in relation to DSM V Substance-Related and Addictive Disorders (SRAD) symptom criterion or clinical impairment/distress. The YFAS has been tested to be psychometrically sound. One study using the YFAS found that nearly 20% of obese persons tested positive for food addiction (FA), yet few if any interventions to address obesity have specifically targeted individuals who test positive for FA.

Empirical evidence is growing for the idea that food addiction may be a contributor to obesity and eating-related problems (Gearhardt, Corbin, & Brownell, 2009a,b). This hypothesis proposes that highly processed foods, high in fat and sugar (HPFS) (e.g., pizza, chocolate, chips), may be capable of triggering an addictive response in individuals with vulnerable characteristics (e.g., impulsivity). Early evidence in animal and human studies suggests that HPFS foods may activate reward related neural circuitry in a similar manner as drugs of abuse. Additionally, behavioral indicators of substance-use disorders, such as loss of control and use despite negative consequences, have been observed in response to HPFS foods. Shared mechanisms (e.g., reward dysfunction, emotion regulation difficulties) and genetic profiles also appear to contribute to both food addiction and substance-use disorders. Thus, existing evidence demonstrates biological and behavioral parallels between individuals with food addiction and substance-use disorders and suggests that HPFS foods may be most likely to have an addictive potential for some individuals.

The Yale Food Addiction Scale (YFAS) is currently the only validated measure to assess symptoms of food addiction. The current version is the YFAS 2.0 is a 35-item self-report questionnaire that applies the DSM-5 diagnostic criteria for substance-use disorders to consumption of HPFS foods. The YFAS 2.0 provides two scoring options: a symptom count (a sum of the eleven diagnostic criteria) and a diagnostic threshold that reflects the criteria for a substance dependence diagnosis (the presence of two or more symptoms plus clinically significant impairment or distress).

The YFAS has good internal consistency ranging from  $\alpha = .76.92$  and demonstrates convergent validity with measures of eating pathology (e.g., emotional eating, food craving) and incremental validity in predicting binge eating frequency above and beyond existing measures. The YFAS has been used to assess food addiction in both community and treatment-seeking samples. Reducing highly processed foods, especially those high in fat and sugar Highly processed foods that are high in fat and sugar (HPFS) are typically low-nutrient simple carbohydrates (LNSC). There is growing recognition that the nature of carbohydrates consumed is an important dietary consideration. A key to healthy eating is reducing consumption of LNSC(e.g., sugars and starches) in favor of complex carbohydrates [e.g., fruits, vegetables (except potatoes), legumes, and whole grains] and minimally processed proteins (nuts, fresh lean meats).

Low-nutrient simple carbohydrates: LNSC are composed of single chain carbon atoms and are rapidly digested and absorbed, resulting in rapid peaks in blood glucose and insulin, followed by a drop in blood glucose and increased perceptions of hunger. Commonly, these foods have little nutritional value and tend to be high in calories. They include processed and homemade foods made with white flour, sugar, and corn syrup such as white breads, tortillas, cold cereals, pastas, candies, pastries, and sugar-sweetened beverages (e.g. fruit drinks, soda, and sports/energy drinks), many of which are commonly consumed in American households. Particularly concerning is that these foods may have addictive properties, affecting dopamine levels. LNSC contribute to many chronic diseases, including type 2 diabetes, hypertension, cardiovascular disease, obesity, inflammation, and metabolic syndrome, and acute conditions such as hunger, satiety, mood, and glycemic load.

High dietary intake of LNSC is associated with lower HDL cholesterol concentrations, an important coronary risk factor. Obesity itself is also associated with low HDL cholesterol levels, as well as increased triglyceride levels, in both children and adults. Results from interventions limiting LNSC intake show promise, with individual studies showing decreases in one or more variables of energy intake, blood pressure, lipid levels, and weight and improved glucose tolerance and hyperinsulinemia in adults age 18 and older.

Complex carbohydrates and natural fats: There is growing evidence that deriving dietary carbohydrates primarily from complex (e.g., whole fruits and vegetables, legumes, whole grains) rather than simple carbohydrate sources may help reduce the risk of developing or aid in the treatment of cardiovascular disease, type II diabetes, and metabolic syndrome and may aid in weight loss. These benefits are thought to derive from the non-starch polysaccharide, dietary fiber, and possibly other components of these foods. Therefore, limiting HPFS foods and increasing CC and natural fat intake is an integral component of our intervention and is consistent with recommendations advocating intake of slowly absorbed complex carbohydrates rather than rapidly absorbed simple carbohydrates. Healthy fats such as nuts, fresh lean meats, avocados, olive oil are also absorbed slowly and have nutrients important in reducing risk of developing cardiovascular disease, type II diabetes and metabolic syndrome.

Motivational Interviewing to limit HPFS intake and increase CC and natural fat intake The framework for the proposed study was adapted from the Predicting and Changing Behavior Theory (PCBT), which proposes that an individuals' attitudes/beliefs (perceptions toward a behavior), perceived norms (including social pressures within a culture or family), and perceived behavioral control (self-efficacy or belief about the ease or difficulty of performing a behavior) are the primary determinants influencing intention to engage in a particular behavior. The PCBT has been used to predict behaviors such as weight

loss, physical activity, and self-efficacy for healthy eating in American populations. However, few, if any, studies have focused on using this approach to encourage obese Americans to reduce their HPFS intake and increase their CC and natural fat intake in an effort to move them toward self-management of obesity, nor have they assessed the impact of such interventions on their diet and/or biometrics. Our MI intervention with and without pharmacotherapy is designed to effect behavior change by sharing information on the benefits of limiting HPFS intake and increasing CC and natural fat intake (addressing attitudes/beliefs), and providing support to increase perceived behavioral control by decreasing participants ambivalence and barriers (addressing self-efficacy), which will support participants in limiting their HPFS intake and increasing their CC intake. MI is evidence-based, client-centered, and individualized, empowering individuals to establish their own realistic goals for behavior change by emphasizing personal choice and affirming client decisions.

#### Pharmacotherapy for Obesity/Addiction (naltrexone-bupropion)

Recent studies have assessed the efficacy of combination treatments of long-acting acting opioid antagonists (naltrexone) and antidepressant drugs (bupropion) in lowering the body weight of obese patients. Bupropion seems to have a complementary effect of decreasing hunger in combination with naltrexone, producing significant long-term decreases in weight. A multicenter phase III trial was conducted that randomly assigned 1,742 overweight individuals to receive an oral preparation of a sustained release pharmaceutical. The intervention continued for 56 weeks after which mean reduction in body weight was significantly higher in the pharmaceutical groups than placebo groups. Pharmaceutical groups were treated with naltrexone 16 mg plus bupropion and 32 mg naltrexone plus bupropion. In the proposed study, dosing protocols will be followed for treatment of obesity: 1 tablet (90mg/8mg) initially week 1; increase by 1 tablet/day each subsequent week until daily maintenance dose of 2 tablets twice daily (360 mg bupropion/32 mg naltrexone) is achieved at the start of week 4. Use will be discontinued at month 4 if no clinical response is observed.

#### Contribution to Science

This study addresses a critical topic and will contribute to the science of treating obese patients, particularly those with FA as diagnosed by the YFAS. We hypothesize that using a team of interventionists delivering an addiction-adapted MI intervention to support obese patients in reducing their HPFS intake and increasing their CC and natural fat intake will enhance the success of our interventions, thereby helping reduce the incidence of addiction/overweight/obesity, improving biometric measures, and reducing the risk for comorbidities associated with obesity. Use of the YFAS and evaluating the interventions in both obesity phenotypes, is expected to help identify better targeted approaches for addressing self-management of obesity by clients in each phenotype. Though this study focuses on a rural population, investigators anticipate that this approach can be adapted to broader populations, including those in urban settings.

Statistical justification for the total number of subjects needed to complete the research to achieve the scientific objectives.

The prevalence of FA is estimated to be 25% in the population of urban adult women who have a BMI classification of overweight or obese. Using this prevalence along with a medium effect size, a statistical power analysis was performed for sample size estimation with G\*Power 3.1. The design is a stratified four-group design with a pre and post measurement. Stratification by obesity phenotype (positive or negative for FA) will occur first, followed by random assignment to one of four treatment groups [Information Control (dietary and physical activity instruction), MI alone(diet and physical activity instruction supported by MI), MI((diet and physical activity instruction supported by MI+P(Contrave)). Using an  $f = 0.25$ , an  $\alpha = .05$  and  $\text{power} = 0.95$ , the a priori F test, analysis of variance, omnibus, one-way model gives a projected sample size of 252. As a pilot study, this study is underpowered for statistical hypothesis testing, and analyses will focus on descriptive statistics, estimation of effect sizes, and hypothesis generation and a sample of 40 eligible patients will be enrolled (10 in each group). This meets the pilot study guideline of at least 10% of a fully powered trial and remains realistic in terms of time and cost (Hertzog, 2008) while allowing for 50% attrition. It is expected that 25% of the population will meet the criteria of FA and therefore will need to screen and consent a total of 160 participants to reach the 40 people positive for FA. No more than 160 subjects will be consented for the entire pilot study.

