#### Proposed methods/approach

Investigators propose assessing obese clients with the YFAS as part of their intake once they are referred to the Healthy Behaviors Clinic by Regional West physicians/practitioners. A nurse researcher with expertise in MI and a nurse practitioner will perform intake assessments, obtain consent and randomly assign participants in each phenotype (positive or negative for FA) to one of three treatment groups (usual care, individual MI alone, and individual MI with pharmacotherapy). Interventions will occur over 6 months. A clinical psychologist with expertise in the YFAS (University of Michigan) will serve as a consultant on this project and a registered dietitian (University of Nebraska Lincoln) will serve as a co-investigator.

Investigators expect that MI and MI+P and P will be more effective in improving outcome measures than IC. We also expect that response to the treatments will differ between the two obesity phenotypes (those testing positive and those testing negative for FA).

To determine if MI alone or MI+P or P is effective in treating obese patients with and without FA (based on the YFAS) as determined by :

- Higher MI confidence, importance and readiness to change scores
- Reduced intake of foods that are highly processed and high in fat and sugar (HPFS) and increased intake of complex carbohydrate foods(fresh fruits, vegetables, whole grains) and minimally processed proteins (nuts, fresh meats) (ASA24-2016® dietary recall)
- Improved biometric measures (BMI, body composition, waist circumference, and blood pressure)

-To determine whether the two obesity phenotypes (with and without FA) differ in their response to the four treatments.

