**Initial Screening for Eligibility (Suicidal Ideation, Pregnancy test (urine test), Lactation, Recruitment):**  
Participants will be recruited from obese patients referred to the Healthy Behaviors Clinic by Regional West Physicians. Nurse researchers who work at the Healthy Behaviors Clinic will inform potential participants about the study and, if they agree to participate, will consent them.

Both treatment groups, Those who test positive for and those who test negative for FA (food addiction) will be assigned to one of four treatment arms, IC, MI, MI+P and P. All will receive dietary and exercise information. After consenting, each participant will be administered the YFAS to determine their obesity phenotype (positive or negative for FA). Participants within each phenotype will be randomly assigned to one of the intervention (MI or MI+P, or P) or the IC information control (diet and physical activity instruction, which will be no less than current standard of care) treatment groups using a randomization schedule (assignments in numbered, sealed, opaque envelopes; one set for each phenotype) 1:1:1:1 ratio, provided by our statistician, [name]. Phenotype assessment and treatment assignment will continue until the sample size (n=10) is met for each phenotype-treatment group category. Those in the control group will be seen at the same time periods as each treatment group to maintain their interaction time with the clinic. They will receive diet and exercise instruction at each time point.

**Intervention Conditions (MI, MI+P):** MI is theorized to decrease a patient's ambivalence and increase his/her perceived behavioral control (self-efficacy) for limiting HPFS and increasing CC intake by emphasizing personal choice and control in decision-making and by affirming the patient's self-management ability. Interventionist nurses will deliver MI sessions following data collection at baseline, 1, 2, 3, and 4 weeks and 2, 3, 4, 5, and 6 months to promote sustained behavioral change. A written MI algorithm will be used to ensure uniform implementation of the intervention.

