#### Statistical Methods to Analyze Data

Missing data will be evaluated. For summated scales on which fewer than 20% of an individuals responses are missing, the individuals mean on the remaining items may be substituted, as appropriate. For analyses requiring complete data, imputation of missing values using the EM algorithm or multiple imputations will be considered, as appropriate. Scoring algorithms for each instrument will be used per the published use manual. Each statistical test will be conducted at  $p=.05$  level. Data will be analyzed using descriptives (means, medians, standard deviations of scores), independent t-tests, correlation coefficients and analysis of variance. In Aim 1, ANOVA will be used to assess differences between the three treatment groups on the YFAS to determined changes in MI confidence, importance and readiness to change scores as well as ASA24-2016® dietary recall and biometric measures. Correlational analysis will be used to explore the relationships between ASA24-2016® dietary recall and biometric measures. In Aim 2 independent t-test will be used to determine if the positive and negative YFAS groups differ across treatment responses.

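### The reference sample size of 252 belongs to a three-group design (four groups need 280), enrolment is given as both 40 and 80, and the 160-consent cap can clash with the rule to fill every cell

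*Combined protocol and SAP*

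**What the plan says.** The sample size paragraph, at the end of Contribution to Science, states that "The design is a stratified four-group design with a pre and post measurement". Using f = 0.25, alpha = .05 and power = 0.95, it reports that "the a priori F test, analysis of variance, omnibus, one-way model gives a projected sample size of 252". Its bracketed list of arms names only information control, MI and MI with pharmacotherapy.

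The paragraph then calls the study an underpowered pilot and says that "a sample of 40 eligible patients will be enrolled (10 in each group"). It claims to meet a guideline of at least 10% of a full trial while allowing for 50% attrition. With 25% of people expected to be FA-positive, it says the study "will need to screen and consent a total of 160 participants to reach the 40 people positive for FA", and adds: "No more than 160 subjects will be consented for the entire pilot study".

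Initial Screening for Eligibility randomises each phenotype 1:1:1:1 to four arms and says that "treatment assignment will continue until the sample size (n=10) is met for each phenotype-treatment group category".

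Two other places keep three groups. Proposed methods/approach assigns participants "to one of three treatment groups (usual care, individual MI alone, and individual MI with pharmacotherapy"), although its aims include pharmacotherapy alone. Statistical Methods to Analyze Data says "ANOVA will be used to assess differences between the three treatment groups on the YFAS".

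**The concern.** Three things do not fit together.

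1. The reference sample size does not follow from the stated inputs if there are four groups. The three-group wording elsewhere suggests that it was carried over from a design without the pharmacotherapy-alone arm.
2. The enrolment total differs by a factor of two between the sample size paragraph and the recruitment section. No place states 80, and the FA-negative participants whom the recruitment section requires do not appear in the justification.
3. The consent cap equals the number that gives 40 FA-positive people in expectation, with no margin. One instruction says to continue until every cell is full and another says to stop consenting at 160.

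The practical stakes lie in the second and third points. Staff following one section would stop at a different total from staff following the other. Any shortfall at the cap would fall on the FA-positive stratum, on which the comparison of phenotypes depends.

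**Working it through.** **Reference sample size.** The sample size paragraph supplies f = 0.25, alpha = .05, power = 0.95 and a one-way omnibus ANOVA. For k equal groups and total N, the noncentrality is lambda = f² x N = 0.0625 x N, with k − 1 and N − k degrees of freedom. Power is the probability that a noncentral F exceeds the central 95th percentile.

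| k | N | lambda | Power |
|---|---|---|---|
| 3 | 249 | 15.56 | 0.9491 |
| 3 | 252 | 15.75 | 0.9515 |
| 4 | 252 | 15.75 | 0.9260 |
| 4 | 276 | 17.25 | 0.9480 |
| 4 | 280 | 17.50 | 0.9510 |

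The plan's 252 is reproduced exactly as the smallest balanced N for three groups (84 each). For four groups the smallest balanced N is 280 (70 each), 28 more. Other variants were tried for four treatments:
- a factorial main effect or interaction with 3 numerator degrees of freedom in 8 cells: 280
- two-time-point repeated measures with an assumed correlation of 0.5: 212 (between groups) or 76 (within-between)
- power of 0.80 or 0.90: 180 or 232

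None gives 252. The 10% benchmark becomes 28 instead of 25.2.

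**Enrolment total.** The sample size paragraph gives 4 groups x 10 = 40. The recruitment section gives 2 phenotypes x 4 arms x 10 = 80. The consent figure, 40 / 0.25 = 160, treats 40 as the FA-positive count alone. This favours 40 per phenotype, hence 80 overall.

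**Cap against fill rule, on the 80-patient reading.** Let X be the number FA-positive among 160 consents, X ~ Binomial(160, p). Assume that every FA-positive consenter is eligible and randomised; losses after consent would make matters worse. The plan's p is 25%. Background/significance cites nearly 20% in obese persons. A value of 30% is added as an assumption on the favourable side.

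| p | Expected X | 10th percentile | P(X ≥ 40) | P(cells short at cap) |
|---|---|---|---|---|
| 20% | 32 | 26 | 0.07 | 0.93 |
| 25% | 40 | 33 | 0.53 | 0.47 |
| 30% | 48 | 41 | 0.93 | 0.07 |

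The FA-negative cells fill with probability close to 1 throughout. An 80% chance of 40 FA-positive people would need 178 consents at 25% or 223 at 20%.

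**Does the 10% claim survive?** As enrolled, 40 is 40/280 = 14.3%. If 80 are enrolled and half are lost, 40 remain, again 14.3%. With the FA-negative stratum full and FA-positive numbers at the 10th percentile, about (33 + 40)/2 = 36.5 (13.0%) or (26 + 40)/2 = 33 (11.8%) remain, still above 28. The claim would fail only if 40 were the whole trial and the guideline counts completers: 20/280 = 7.1%, or 20/252 = 7.9%.

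**The case against.** The strongest reply concerns weight. The plan says the pilot is underpowered and descriptive, so 252 sets no enrolment number, and 40 enrolled exceeds 10% of either 252 or 280. This stands: alone, the wrong reference figure would be a minor correction. That the calculation was run with three groups is also an inference from an exact match and the leftover wording. The brackets in the arm list of the sample size paragraph are garbled, so that list is weaker evidence than the two explicit mentions of three groups.

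On accrual, it can be said that the cap is unconditional and so naturally binds. But the fill rule is equally unconditional, and nothing ranks one above the other. A reader may well guess that the cap prevails, but the plan should say so.

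Prevalence is uncertain both ways. The 25% refers to urban overweight or obese women and the 20% to obese persons in one study; neither is this clinic's referred population. At 30% the conflict would be rare. The finding does not need the 20% figure, however, since the plan's own 25% gives a conflict nearly half the time.

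Finally, writing 80 doubles the total that the sample size paragraph states. That is fair, and it is why the sponsor must first decide which total was intended.

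**Conclusion.** The point holds in all three parts and should be corrected. The figure of 252 is wrong for the stated four-group design. The right figure is 280, a difference of 28, and 252 across four groups has power 0.926 instead of 0.95. The consequence is small, because only the 10% benchmark rests on it.

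The contradiction between 40 and 80 is the more serious defect. The text best supports 80 (40 per phenotype), but nowhere says so. On that reading, the cap and the fill rule cannot both be met with probability 0.47 at 25% prevalence, assuming no loss between consent and randomisation. The guideline claim is not an error on the 80-patient reading, and the conclusion does not depend on whether the guideline counts completers.

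**What to change.** First decide whether the intended total is 80 or 40. Then:

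- Restate the reference sample size as 280 (70 in each of four groups) and the 10% benchmark as 28.
- Correct the three-group wording to four in the arm list of the sample size paragraph, in Proposed methods/approach and in Statistical Methods to Analyze Data.
- If 80 is intended, replace the enrolment sentence with: *Up to 80 eligible patients will be enrolled, 40 per phenotype and 10 in each of the 8 phenotype-by-treatment cells; about 40 will be retained after 50% attrition if all cells fill.*
- Add: *Accrual ends at 10 per cell or 160 consents, whichever comes first. The FA-positive stratum may fall short of 40 (expected 40 at 25% prevalence and 32 at 20%; 10th percentiles 33 and 26).*
- If 40 was meant as the whole trial, change the 10-per-category rule in the recruitment section instead, and restate the consent arithmetic to match.

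As an option, if the FA-positive envelopes are not already blocked, small permuted blocks would keep the arms balanced should accrual stop at the cap.

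The cost is text only. The 80-patient wording needs no more patients than the recruitment section already requires and no more consents than the cap allows, but it doubles the total now stated in the sample size paragraph. It also states openly that the FA-positive stratum may fall short.

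### The benchmark of 252 at 95% power is a three-group, one-way figure with no phenotype factor, so it does not give 95% power for four arms compared within each phenotype

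*Combined protocol and SAP*

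**What the plan says.** The Summary sets the purpose as judging four treatments "for improving outcome measures within each phenotype". The sample-size paragraph, at the end of Contribution to Science, describes the layout: "The design is a stratified four-group design with a pre and post measurement", and "Stratification by obesity phenotype (positive or negative for FA) will occur first, followed by random assignment to one of four treatment groups". It then gives the size of a fully powered trial: "the a priori F test, analysis of variance, omnibus, one-way model gives a projected sample size of 252". The inputs are f = 0.25, alpha = .05 and power = 0.95.

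The same paragraph states that the pilot is underpowered for hypothesis testing and will concentrate on description and effect sizes. It enrols 40 patients, 10 per group, and justifies this as at least 10% of a fully powered trial. It expects to consent 160 people so as to find 40 who are FA-positive.

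The Initial Screening for Eligibility section sets equal cells: "Phenotype assessment and treatment assignment will continue until the sample size (n=10) is met for each phenotype-treatment group category". Elsewhere the number of arms is three. Proposed methods/approach assigns patients "to one of three treatment groups (usual care, individual MI alone, and individual MI with pharmacotherapy"), and in Statistical Methods to Analyze Data "ANOVA will be used to assess differences between the three treatment groups".

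**The concern.** A one-way omnibus ANOVA sizes a single comparison among groups. It has no place for phenotype, so every patient counted in N serves that one comparison. The purpose in the Summary needs the comparison made twice, once in FA-positive and once in FA-negative patients, and randomisation is arranged to allow this. A figure from the one-way routine carries over only if it is read as the size of one phenotype and uses the right number of arms.

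The 252 is the plan's only statement of what a fully powered trial would need, and it is the denominator of the 10% justification for the pilot. Anyone who sizes a later trial from this paragraph, taking 252 as a total, would believe that power within each phenotype is 95% when it is well below that.

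**Working it through.** **Inputs.** f = 0.25, alpha = .05 and power = 0.95 come from the sample-size paragraph. The number of arms k is 4 (Summary, sample-size paragraph, Initial Screening) or 3 (Proposed methods/approach, Statistical Methods). Allocation between arms is equal within phenotype (Initial Screening). No split of 252 between phenotypes is stated. An equal split is an assumption, modelled on the pilot's equal cells; the alternative shown is the plan's 25% FA prevalence.

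**Formula.** Power = P(F′ > F crit), where F′ is noncentral F with k − 1 and N − k degrees of freedom and λ = N × f² = 0.0625 N, and F crit is the 95th percentile of the central F.

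**Step 1, reproduce 252.** The smallest balanced N for 95% power is 210 for k = 2, 252 for k = 3, 280 for k = 4, 324 for k = 6 and 360 for k = 8. Only k = 3 returns 252 (λ = 15.75, power 95.1%). With four arms, 252 gives 92.6%.

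**Step 2, power within a phenotype.**

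| Patients in the phenotype | How it arises | λ | Four arms | Three arms |
|---|---|---|---|---|
| 252 | 252 is per phenotype | 15.75 | 92.6% | 95.1% |
| 126 | 252 is the total, split equally | 7.875 | 63.1% | 69.9% |
| 63 | FA-positive, 25% of 252 | 3.94 | 33.2% | 39.2% |
| 189 | FA-negative, 75% of 252 | 11.81 | 82.5% | 87.2% |
| 140 | 280 is the total, split equally | 8.75 | 68.4% | not needed |

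If 252 is the total, the smaller phenotype cannot exceed 126 under any split, so 63.1% (four arms) or 69.9% (three arms) is its ceiling. Using an error term pooled over both phenotypes raises the four-arm figure only to 63.9%.

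**Step 3, separate the two causes.** With the number of arms held fixed, the split alone takes power from 92.6% to 63.1% (four arms) or from 95.1% to 69.9% (three arms). The arm count alone takes it from 95.1% to 92.6%.

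**Step 4, size for 95% within each phenotype.** Four arms: 280 per phenotype, 2 × 280 = 560. Three arms: 252 per phenotype, 2 × 252 = 504.

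**Step 5, the 10% guideline.** As stated: 40/252 = 15.9%. With matched bases for four arms: 40/280 = 14.3% per phenotype, or 80/560 = 14.3% overall, where 80 = 8 cells × 10. If 40 covers both phenotypes: 40/560 = 7.1%. These ratios count enrolled patients; the 50% attrition that the plan allows for would halve each of them.

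**The case against.** The strongest reply is that 252 may already be a per-phenotype figure. Four arms of 10 make 40 in one phenotype, and 160 × 0.25 = 40 is the plan's own count of FA-positive patients. On that reading 40 and 252 share a basis, nothing is halved, and four-arm power is 92.6%. This stands as a possible reading. It still falls short of 95%, and the plan does not say that a full trial would need two such samples.

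Second, the one-way, three-group calculation agrees with the analysis section, where Aim 1 compares three groups and no phenotype factor is stated. That is true, but it agrees with a three-arm design while the Summary and the randomisation text describe four.

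Third, another objective is "To determine whether the two obesity phenotypes (with and without FA) differ in their response to the four treatments". For an interaction of f = 0.25, a total of 252 gives 92.6% power in a 2 × 4 layout. That supports 252 as a rough size for the interaction question; it does not answer efficacy within a phenotype.

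Fourth, 252 is never enrolled, and the plan openly disclaims power for testing. This limits the weight of the point to a stated benchmark and the ratio built on it.

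The 25% prevalence is not an input to the ANOVA routine, but it is used, to derive the 160 to be consented, so it should not be counted as a further error.

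**Conclusion.** The 95% attached to 252 does not hold for four arms compared within each phenotype, whichever way 252 is read. The shortfall is small if 252 is per phenotype (92.6%; 280 needed). It is large if 252 is the total: at most about 63% in the smaller phenotype, and about 33% for FA-positive patients at 25% prevalence. These figures rest on the plan's f and alpha and on four arms. The 33% also assumes recruitment at the stated prevalence.

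A reader might infer two stronger conclusions that the documents do not support.

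- *That true power is 63% rather than 95%.* This sets a four-arm figure against a three-arm one, and it takes 252 to be a total, which the plan never states.
- *That 40 patients fail the 10% guideline.* This holds only if 40 covers both phenotypes. On matched bases the enrolled ratio is 14.3% and passes. The doubt comes from the separate conflict between 40 in the sample-size paragraph and the 80 implied by 10 in each phenotype-treatment cell.

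**What to change.** In the sample-size paragraph, recompute for four arms and state what the figure covers. Either of two wordings would do.

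- *Per phenotype:* for four arms compared within each phenotype (f = 0.25, alpha = .05, power = .95), a fully powered trial needs 280 per phenotype, 560 in total.
- *Pooled:* 280 in total gives 95% power for four arms pooled over phenotypes; with 140 per phenotype, power within each is about 68%.

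Reconcile the three-group wording in Proposed methods/approach and in Statistical Methods with the four declared arms. Say whether 40 is per phenotype or the whole pilot, given the 80 implied by the cell sizes. Then restate the 10% guideline with numerator and denominator on the same basis, and say whether it counts patients enrolled or completing.

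The cost is one recalculation and some wording. No change to pilot enrolment is needed, though the benchmark rises and the ratio becomes less favourable than the 15.9% that 40/252 implies.
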